## 1 PROTOCOL SUMMARY

Trial Title:	A 4-year non-interventional, multicentre, prospective study to evaluate effectiveness, adherence and safety of cladribine tablets in patients with highly active relapsing multiple sclerosis in Slovakia
Protocol No:	MS700568-0102
Sponsor	Nezisková organizácia CARMENTA [name] [name] Slovakia
Coordinating Investigator:	[name]. [name] First Department of Neurology, Faculty of Medicine, Comenius University, Nemocnica Stare Mesto, [name], Slovak Republic
Location:	Slovakia
Medicinal Product:	Cladribine (MAVENCLAD®), oral tablets. Decision to initiate treatment with cladribine has to be made before patient is enrolled to the study. Dosing and administration of cladribine will be performed in accordance with MAVENCLAD® Summary of Product Characteristics (SmPC) applicable in Slovakia including management of concomitant medication. Administration and choice of rescue therapy will be fully in discretion of the physician and according to standard of care.
Rationale:	Cladribine is an oral disease modifying drug (DMD) approved for the treatment of adult patients with highly active relapsing multiple sclerosis. Cladribine is a nucleoside analogue of deoxyadenosine that has been shown to exert long-lasting effects by preferentially targeting lymphocytes and the autoimmune processes involved in the pathophysiology of MS. Of note, Cladribine 10 mg tablets treatment consists in 16 to maximum 20 days of oral dosing in the first 2 years with no further treatment required in the next 2 years. The aim of the present study is to evaluate clinical benefits of Cladribine 10 mg tablets treatment in real-life settings of Slovakian standard care as this information is missing to date.
Study Objectives:	Primary 

To assess the effectiveness of Cladribine 10 mg tablets in the real life settings by the Annualized Relapse Rate (ARR) during the 4-year observational period.

 A relapse is defined as meeting the following criteria:

	
Secondary
 
 
• To evaluate disability progression occurrence during the 4-year study observational period.
 
• To evaluate changes of Expanded Disability Status Scale (EDSS) during the 4-year study observational period.
 
• To evaluate the MRI measures performed yearly during the 4-year study observational period.
 
• To evaluate the proportion of patients receiving rescue therapy according to the local standards of care during the 4-year observational period.
 
• To evaluate the patient adherence to Cladribine 10 mg tablets treatment after both dosing periods in year 1 and 2.
 
• To evaluate association of patient adherence to treatment with relapse occurrence during the 4-year study observational period.
 
• To evaluate safety of Cladribine 10 mg tablets treatment during the 4-year study observational period.
 

Study Design:
	
This is a non-interventional, multicentre, prospective, study for patients with highly active relapsing MS for whom Cladribine 10 mg tablets therapy was indicated independently before enrolment to the study.
 
Eligible subjects will undergo all visits and procedures before and during the treatment as per local standards and Cladribine 10 mg tablets administration will be in accordance with approved SmPC. Protocol does NOT define any mandatory

1. Neurological abnormality, either newly appearing or re-appearing, with abnormality specified by both
  - a. Neurological abnormality separated by at least 30 days from onset of a preceding clinical event
  - and*
  - b. Neurological abnormality lasting for at least 24 hours
2. Absence of fever or known infection (fever with temperature (axillary, orally or intrauricular) > 37.5°C)
3. Objective neurological impairment, correlating with the subject's reported symptoms, defined as either
  - a. Increase in at least one of the functional system (FS) scores of the EDSS
  - or
  - b. Increase of the total EDSS score

The occurrence of paraesthesia, fatigue, mental symptoms, and/or vegetative symptoms without any additional symptom will not be classified as an MS clinical relapse.

 The time to sustained progression of disability is defined as the time to a sustained increase (for at least 3 months) of at least 1 point in the EDSS score compared to baseline for all subjects with an EDSS ≤5.0 or an increase of at least 1.5 points if the baseline EDSS score was 0.

	
assessment. Assessments schedule is approximate, all described assessments and events will be collected and finally statistician will analyse them within relevant window for respective visit. According to standard practice in Slovakia, patients treated by DMD visit their physician at MS centre at least once per year (as required by payers) but usually every 3 months.
 
Patients will be followed up to 4 years after the first dose of Cladribine 10 mg tablets. Patients with low lymphocyte count to start Cladribine 10 mg tablets therapy after the first year are allowed to postpone second cycle up to 6 months until lymphocyte count recovers (as per SmPC) and therefore their participation may take up to 4.5 years.


Patient Selection Criteria:
	
Total expected number of participating patients: 100
 
Inclusion Criteria:
 
 
• Age ≥18 years.
 
• Patients for whom start of Cladribine 10 mg tablets therapy for highly active relapsing MS (relapsing-remitting multiple sclerosis – RRMS, or secondary progressive multiple sclerosis - SPMS) has been indicated independently before signing informed consent.
 
• Patient fulfils following local indication criteria for Cladribine 10 mg tablets treatment as applicable in standard of care:             
 
○ 1 severe relapse treated by corticosteroids or EDSS score increase by at least 1 grade during the previous year and at least 1 T1Gd+ lesion or 9 or more T2 lesions during the treatment by at least one other DMD,
 
 
OR
 
 
○ 2 or more disability causing relapses treated by corticosteroids during the previous year and treated or untreated by the other DMD. MS diagnosis has to be confirmed by cerebrospinal fluid examination.
 
 
 
• Signed informed consent.
 
• Ability to communicate with investigator and study staff and to comply with their instructions for the entire length of the study participation.
 
 
Exclusion criteria:
 
 
• Other type of MS than highly active relapsing MS.
 
• Contraindications listed in Cladribine 10 mg tablets
 

	
SmPC.
 
 
• Moderate or severe hepatic impairment (Child-Pugh score >6)
 
• Patient (men and women of childbearing potential) is unable or unwilling to practice birth control during Cladribine 10 mg tablets treatment and for at least 6 months after the last dose.
 
• Concurrent participation in any interventional study.
 

Recruitment modalities:
	
Site selection: 12 centres specialized in the care of patients with MS across Slovakia
 
Patient selection: Physician will offer participation to all consecutive patients meeting eligibility criteria during the enrolment period. Competitive enrolment is allowed.


Study endpoints:
	
Primary:
 
 
• ARR at 48 months
 
 
Secondary:
 
 
• Proportion of relapse-free patients at 24 and 48 months
 
• ARR at 24 months
 
• The time to sustained progression of disability from baseline up to 24 and 48 months
 
• Time to the first relapse from baseline up to 48 months
 
• Time to the second relapse from baseline up to 48 months
 
• Changes in mean number of T1 Gd+ lesions per MRI scan taken at 12, 24, 36 and 48 months compared to baseline
 
• Changes in mean number of active T2-weighted lesions per MRI scan taken at 12, 24, 36 and 48 months compared to baseline
 
• Changes in level of disability as measured by EDSS at 6, 12, 18, 24, 30, 36, 42 and 48 months compared to baseline
 
• No evidence of disease activity (NEDA-3) at 24 and 48 months
 
• The proportion of patients receiving rescue therapy according to local standards of care from baseline up to 48 months
 
• Patient adherence to Cladribine 10 mg tablets treatment after both dosing periods as assessed at 3 and 15 months (by counting used tablets from original
 

	
packages as patients will be asked to bring them to the site).
 
 
• Frequency of adverse events (AE) interviewed or reported spontaneously by the patients or as noted on physical, MRI or laboratory examinations up to month 48
 
• Percentage of patients with at least 1 Common Terminology Criteria for Adverse Events (CTCAE) grade 3 or 4 Lymphocyte Toxicity up to month 48
 
• Median time to recovery from grade 3 or 4 Lymphocyte Toxicity
 
• Percentage of patients who developed herpes zoster infections or malignancies up to month 48
 


Collected Data:
	
V1 - Pre-dose Year 1 Visit
 
Date of visit, date of ICF signature (if different), meeting of eligibility criteria (yes/no)
 
Basic demographic data:
 
 
• Year of birth
 
• Gender
 
 
Baseline characteristics:
 
 
• Relevant medical history
 
• Relevant concurrent diseases/concomitant medications
 
 
Condition of MS:
 
 
• Date of MS diagnosis
 
• Medical history related to MS
 
• Previous MS therapy
 
• Number of relapses in the last 12 months
 
• Current EDSS score
 
• Current MRI status (within 3 months)
 
 
Pre-treatment requirements
 
 
• Is patient eligible to start Cladribine 10 mg tablets therapy as per SmPC? (yes/no)
 
• Patient weight
 
• Lymphocyte count
 
• Number of Cladribine 10 mg tablets to be used in the whole treatment course year 1
 
 
V2 - Visit Month 3 Year 1 (2 months after the first dose of Cladribine 10 mg tablets in Year 1)

	

• Visit date

• Date of Cladribine 10 mg tablet therapy start Number of Cladribine 10 mg tablets really used the whole treatment course year 1

• Lymphocyte count

• Any relapse and rescue therapy from the last visit

• Any AE from the last visit

• Concomitant medication (only corticosteroids, myorelaxants, analgesics, antidepressants, anxiolytics) from the last visit

 
V3 - Visit Month 7 Year 1 (6 months after the first dose of Cladribine 10 mg tablets in Year 1)
 

• Visit date

• Lymphocyte count

• EDSS score

• Any relapse and rescue therapy from the last visit

• Any AE from the last visit

• Concomitant medication (only corticosteroids, myorelaxants, analgesics, antidepressants, anxiolytics) from the last visit

 
V4 - Pre-dose Year 2 (12 months after the first dose of Cladribine 10 mg tablets in Year 1; For patients with lymphocyte count bellow 800 cells/mm^3 the treatment course in year 2 must be delayed for up to 6 months to allow for recovery of lymphocytes. For these patients will be postponed until recovery - up to maximum of 6 months).
 

• Visit date

• Is patient eligible to continue Cladribine 10 mg tablets therapy as per SmPC? (yes/no)

• MRI status

• EDSS score

• Patient weight

• Lymphocyte count

• Number of Cladribine 10 mg tablets to be used in the whole treatment course year 2

• Any relapse and rescue therapy from the last visit

• Any AE from the last visit

• Concomitant medication (only corticosteroids, myorelaxants, analgesics, antidepressants, anxiolytics) from the last visit

--	---

	
V5 - Visit Month 3 Year 2 (2 months after the first dose of Cladribine 10 mg tablets in Year 2)
 

• Visit date

• Date of Cladribine 10 mg tablet therapy start Number of Cladribine 10 mg tablets really used in the whole treatment course year 2

• Lymphocyte count

• Any relapse and rescue therapy from the last visit

• Any AE from the last visit

• Concomitant medication (only corticosteroids, myorelaxants, analgesics, antidepressants, anxiolytics) from the last visit

 
V6 - Visit Month 7 Year 2 (6 months after the first dose of Cladribine 10 mg tablets in Year 2)
 

• Visit date

• Lymphocyte count

• EDSS score

• Any relapse and rescue therapy from the last visit

• Any AE from the last visit

• Concomitant medication (only corticosteroids, myorelaxants, analgesics, antidepressants, anxiolytics) from the last visit

 
V7 - Visit Month 12 Year 2/month 1 Year 3 (12 months after the first dose of Cladribine 10 mg tablets in Year 2)
 

• Visit date

• MRI status

• EDSS score

• Any relapse and rescue therapy from the last visit

• Any AE from the last visit

• Concomitant medication (only corticosteroids, myorelaxants, analgesics, antidepressants, anxiolytics) from the last visit

 
V8 - Visit Month 7 Year 3 (18 months after the first dose of Cladribine 10 mg tablets in Year 2)
 

• Visit date

• EDSS score

• Any relapse and rescue therapy from the last visit

• Any AE from the last visit

• Concomitant medication (only corticosteroids, myorelaxants, analgesics, antidepressants,

--	--

	
anxiolytics) from the last visit
 
V9 - Visit Month 12 Year3/month 1 Year 4 (24 months after the first dose of Cladribine 10 mg tablets in Year 2)
 
 
• Visit date
 
• MRI status
 
• EDSS score
 
• Any relapse and rescue therapy from the last visit
 
• Any AE from the last visit
 
• Concomitant medication (only corticosteroids, myorelaxants, analgesics, antidepressants, anxiolytics) from the last visit
 
 
V10 - Visit Month 7 Year 4 (30 months after the first dose of Cladribine 10 mg tablets in Year 2)
 
 
• Visit date
 
• EDSS score
 
• Any relapse and rescue therapy from the last visit
 
• Any AE from the last visit
 
• Concomitant medication (only corticosteroids, myorelaxants, analgesics, antidepressants, anxiolytics) from the last visit
 
 
EOS - Visit Month 12 Year 4 (36 months after the first dose of Cladribine 10 mg tablets in Year 2)/Premature Withdrawal Visit
 
 
• Visit date
 
• MRI status
 
• EDSS score
 
• Any relapse and rescue therapy from the last visit
 
• Any AE from the last visit
 
• Concomitant medication (only corticosteroids, myorelaxants, analgesics, antidepressants, anxiolytics) from the last visit
 
• Reasons for premature withdrawal if applicable
 

Statistical Considerations:
	
Analysis of collected data is based on descriptive statistics including absolute and relative frequencies of discrete variables. Continuous variables are described by count (without missing), mean and its 95% confidence interval (CI), standard deviation, median, minimum, and maximum. Discrete variables are described by count (absolute frequency), and percentages (relative frequency).
 
Missing data will not be replaced.
 
Analysis of primary endpoint - ARR at 48 months - will be

	
performed using descriptive statistics: count (without missing), mean and its 95% confidence interval, standard deviation, median, minimum and maximum.
 
Interim analysis will be performed when all patients complete visit at month 25 or withdraw earlier.
 
A sample size of 85 subjects will have more than 80% power to achieve a supposed ARR 0.14 (95 % CI: 0.12–0.17) using a 2-sided significance level of 0.05. Assuming a 15% drop-out rate, a total of 100 patients will be targeted for this study.

Study Timelines:	
First patient first visit: April 2020
 
Last patient first visit: August 2021
 
End of data collection: October 2025
 
Enrolment period: 18 months
 
Participation of each patient will take approximately: 4 years (48 months). However, patients who postpone their therapy in year 2 due to low lymphocyte count up to 6 months (as per SmPC) are allowed to take part for up to 4.5 years in this case.

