## 7 EVALUATION CRITERIA

### 7.1 Primary endpoint

- ARR at 48 months

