## 12 STATISTICAL METHODOLOGY

Based on this part of the protocol, a statistical analysis plan (SAP) will be created. The statistical analysis plan will be processed and approved before closing the database. Possible changes in the evaluated parameters or in the methods of analysis against the protocol will be described and justified in SAP. The statistical analysis is performed in IBM SPSS software.

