### 12.1 Sample Size

A sample size of 85 subjects will have more than 80% power to achieve a supposed ARR 0.14 (95 % CI: 0.12–0.17) using a 2-sided significance level of 0.05. Assuming a 15% drop-out rate, a total of 100 patients will be targeted for this study.

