### 12.2 Data Analysis

Analysis of collected data is based on descriptive statistics including absolute and relative frequencies of discrete variables. Continuous variables are described by count (without missing), mean and its 95% confidence interval (CI), standard deviation, median, minimum, and maximum. Discrete variables are described by count (absolute frequency), and percentages (relative frequency).

Missing data will not be replaced.

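### The primary ARR is planned as an equally weighted mean of per-patient rates, which is biased if patients leave the study because of a relapse

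*Protocol*

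**What the plan says.** The primary endpoint in Section 7.1 is "ARR at 48 months". The protocol gives no formula or exposure denominator for it.

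The Statistical Considerations part of Section 1 names the primary analysis, described there as "performed using descriptive statistics: count (without missing), mean and its 95% confidence interval, standard deviation, median, minimum and maximum". Section 12.2 gives the same list for every continuous variable and adds: "Missing data will not be replaced".

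Three other places bear on the point:

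- Section 12.1 allows for unequal follow-up: "Assuming a 15% drop-out rate, a total of 100 patients will be targeted for this study".
- Section 6.3.3 lists three reasons for withdrawal: withdrawn consent, loss to follow-up, and the start of a new disease modifying drug.
- Section 8.2 and Table 8-1 collect relapses since the last visit at the premature withdrawal visit too, so early leavers do contribute relapse data.

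**The concern.** A standard deviation, median, minimum and maximum exist only if each patient has his or her own ARR. The primary estimate is therefore a plain average of individual rates. Someone observed for six months counts as much as someone observed for four years. That the ARR is formed per patient is an inference from the list of statistics, not something the protocol states outright, but no other reading gives those statistics a meaning.

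Equal weighting matters when the length of follow-up depends on the outcome. The patients have highly active disease, and a relapse is a plausible reason to change drug. Under Section 6.3.3 that change ends observation. Patients who leave this way have a relapse in the numerator and a short time in the denominator. If they are kept, they pull the mean up. If their 48-month ARR is treated as missing and not replaced, relapsing patients drop out of the calculation and the mean falls. The protocol does not say which applies. At stake is the one number the study is built to report.

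**Working it through.** **The plan's own figure.** 85 / (1 − 0.15) = 100, so the enrolment target reproduces.

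**One patient by hand.** One relapse with exit at six months gives 1 / 0.5 = 2.0 per year, which adds 2.0 / 100 = 0.02 to a 100-patient mean. The same single relapse over four years gives 1 / 4 = 0.25 per year and adds 0.25 / 100 = 0.0025. The first patient has eight times the influence of the second.

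**Simulation inputs**

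- From the protocol: ARR 0.14 and 15% drop-out (Section 12.1); four years of follow-up (Section 5.1).
- Assumed, because the protocol gives no value: the probability *p* that a relapse leads to exit, a three-month delay from relapse to exit, and between-patient variation in the true rate (none, or gamma with variance factor 1).
- Unrelated drop-out is added in some scenarios as an exponential time reaching the stated percentage by year 4. Each scenario has 200,000 patients.

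**Estimators**, with yᵢ relapses over tᵢ years:

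- unweighted mean: (1/n) Σ(yᵢ/tᵢ)
- completers only: the same mean restricted to tᵢ = 4
- pooled rate: Σyᵢ / Σtᵢ
- negative binomial: exp(β₀) from log E(yᵢ) = β₀ + log tᵢ

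**Results, true ARR 0.14.** Each pair is no variation / variance factor 1.

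| Scenario | Total drop-out | Unweighted mean | Completers only | Pooled | Negative binomial |
|---|---|---|---|---|---|
| 15% unrelated, *p* = 0 | 15% / 15% | 0.140 / 0.140 | 0.140 / 0.140 | 0.140 / 0.140 | 0.140 / 0.140 |
| 10% unrelated, *p* = 0.10 | 14% / 14% | 0.162 / 0.164 | 0.127 / 0.120 | 0.139 / 0.137 | 0.139 / 0.140 |
| 7.5% unrelated, *p* = 0.20 | 17% / 16% | 0.188 / 0.186 | 0.114 / 0.103 | 0.140 / 0.134 | 0.141 / 0.140 |
| none unrelated, *p* = 0.35 | 17% / 15% | 0.225 / 0.218 | 0.094 / 0.079 | 0.140 / 0.129 | 0.141 / 0.139 |

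**Effect of the delay** (*p* = 0.30, all exits after relapse, 13–15% leaving). The unweighted mean is 0.250–0.257 for a one-month delay, 0.210–0.213 for three months and 0.184–0.187 for six months. Completers-only means are 0.085–0.104 throughout.

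**Precision when drop-out is unrelated** (100 patients, 15% drop-out). The standard error is 0.0229 for the unweighted mean and 0.0192 for the pooled rate without variation, and 0.0267 and 0.0244 with it.

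**Scale.** With 85 × 4 = 340 patient-years, the Poisson 95% half-width around 0.14 is 1.96 × √(0.14/340) = 0.040. The upward error in the table runs from 0.162 − 0.140 = 0.022 to 0.225 − 0.140 = 0.085, that is, from about half to about twice that half-width.

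**The case against.** The strongest reply is that an unweighted mean of rates is not biased in itself. That is correct. With a constant rate and drop-out unrelated to relapse, the expected value of yᵢ/tᵢ is the true rate, and the first row of the table shows every estimator at 0.140. A reader might infer that the planned mean is wrong in any event; it is not. The bias needs relapse-related withdrawal, and Section 6.3.3 makes that plausible without proving it. Section 6.3.3 also lists withdrawn consent and loss to follow-up, so the *p* = 0.35 row, where every departure follows a relapse, is the extreme of the range shown.

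A second reply is that the ARR denominator and the handling of early leavers commonly belong in the SAP, which is not shown. That stands for those details. But the protocol has itself chosen the summary statistic, and Section 12 requires the SAP to justify any departure from it.

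Three further inferences are tempting and not supported:

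- **That sizing on 85 of 100 means a completers-only analysis.** It is ordinary inflation for drop-out. The phrase about missing values qualifies the count, and collecting relapses at the withdrawal visit suggests that early leavers' data are meant to be used. Dropping them is one possible reading, not a stated rule.
- **That the choice would be made after the interim results.** Section 12 says "The statistical analysis plan will be processed and approved before closing the database", which sets only a latest date. Nothing shows when the SAP was approved.
- **That handling of early leavers matters more than the drug.** There is no comparator, so no drug effect is available to compare with.

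**Conclusion.** The point holds, on a condition. Followed as written, the plan gives a primary ARR that is unweighted for follow-up time, in a study whose own withdrawal rule can end follow-up because of the outcome. If some relapses lead to exit, the estimate is too high with early leavers kept and too low with them left out.

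For *p* between 0.10 and 0.35, a three-month delay and total drop-out of about 14–17%, a true ARR of 0.14 is reported as about 0.16–0.22 or about 0.08–0.13. At the mild end both values stay within the 0.12–0.17 interval in Section 12.1. From *p* = 0.20 upwards they fall outside it on opposite sides. If withdrawal is unrelated to relapse, the only cost is precision.

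The direction follows from the arithmetic. The size rests on the assumed exit probability, delay and between-patient variation, none of which the protocol gives.

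**What to change.** Replace the primary analysis wording in Section 1, and add it to Section 12.2, to this effect: the ARR at 48 months and its 95% CI are estimated together from one intercept-only negative-binomial model of relapse counts, with log follow-up time as offset. All treated patients are included, early leavers among them. Time runs from first dose to month 48 or last contact, whichever is earlier. Use the same model for ARR at 24 months, with month 24 as the limit.

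Report total relapses divided by total patient-years alongside. It should not supply the point estimate while the model supplies the interval: when rates vary between patients and those with high rates leave early, the two differ (0.129 against 0.139 in the *p* = 0.35 scenario), and the estimate would not belong to its own CI. The model does well in these simulations partly because they share its assumptions of a constant rate and gamma variation, so the pooled rate is a useful check.

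Keep the per-patient mean, SD, median, minimum and maximum as description only.

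The cost is protocol and SAP wording and a little model work. First-dose date, visit dates and relapses since the last visit are already collected, including at premature withdrawal, so no new data are needed.
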